### Weight and BMI:

6. Total body weight  $> 50$  kg (110 lbs) and BMI  $\geq 24.5$  to  $\leq 45.5$  kg/m^2.

**Note:** For non-diabetic participants with obesity (if enrolled) BMI  $> 30.5$  to  $\leq 45.5$  kg/m^2.

### Informed Consent:

7. Capable of giving signed informed consent as described in [Appendix 1](#), which includes compliance with the requirements and restrictions listed in the ICD and in this protocol.

## 5.2. Exclusion Criteria

Participants are excluded from the study if any of the following criteria apply:

### Medical Conditions:

1. Evidence or history of clinically significant hematological, renal, endocrine, pulmonary, gastrointestinal, hepatic, psychiatric, neurological, dermatological, or

- allergic disease (including drug allergies but excluding untreated, asymptomatic, seasonal allergies at the time of dosing).
- Participants who have chronic conditions other than T2DM and obesity (for example, hypercholesterolemia or hypertension) but are controlled by either diet or stable doses of 2 or fewer medications may be included (for example, a participant with hypercholesterolemia on appropriate treatment is eligible). See [Section 6.8](#) for further information on concomitant medications.
  - For non-diabetic participants with obesity (if enrolled), a medical history of T2DM.
2. Diagnosis of type 1 diabetes mellitus or secondary forms of diabetes.
  3. Evidence or history of clinically significant cardiovascular disease. In particular, history of myocardial infarction, unstable angina, arterial revascularization, stroke, New York Heart Association Functional Class II-IV heart failure, or transient ischemic attack within 6 months of screening.
  4. Any malignancy not considered cured (except basal cell carcinoma and squamous cell carcinoma of the skin); a participant is considered cured if there has been no evidence of cancer recurrence in the previous 5 years.
  5. Acute pancreatitis or history of chronic pancreatitis.
  6. Acute gallbladder disease.
  7. Any condition possibly affecting drug absorption (eg, prior bariatric surgery, gastrectomy, or any area of intestinal resection, active inflammatory bowel disease or pancreatic insufficiency).
  8. Personal or family history of MTC or MEN2, or participants with suspected MTC per the investigator's judgement.
  9. Other medical or psychiatric condition including recent (within the past year) or active suicidal ideation/behavior or laboratory abnormality that may increase the risk of study participation or, in the investigator's judgment, make the participant inappropriate for the study.

**Prior/Concomitant Therapy:**

10. Participants who have received any vaccine within the 1 week prior to admission to the CRU.
11. Use of any prohibited concomitant medication(s) or those unwilling/unable to use a permitted concomitant medication(s). Refer to [Section 6.8](#) and [Appendix 8](#).

### **Prior/Concurrent Clinical Study Experience:**

12. Previous administration with an investigational drug within 30 days (or as determined by the local requirement) or 5 half-lives preceding the first dose of study intervention used in this study (whichever is longer).
13. Known prior participation (ie, randomized and received at least 1 dose of investigational product) in a trial involving PF-07081532. Note that a given individual may only participate in one cohort of this study.

### **Diagnostic Assessments:**

14. A positive urine drug screen at screening or admission.

**Note:** Participants who have been medically prescribed benzodiazepines and report the use of these drugs to the investigator at the screening visit may be allowed to participate if approved by the sponsor.

15. Positive testing at screening for HIV, HBsAg, HBcAb, HBsAb or HCVAb. Positive COVID-19 test at screening or admission.

**Note:** A positive HBsAb due to hepatitis B vaccination is permissible.

16. Screening supine BP  $\geq 160$  mm Hg (systolic) or  $\geq 100$  mm Hg (diastolic) following at least 5 minutes of supine rest.

If BP is  $\geq 160$  mm Hg (systolic) or  $\geq 100$  mm Hg (diastolic), the BP should be repeated 2 more times and the average of the 3 BP values should be used to determine the participant's eligibility.

17. Screening 12-lead ECG that demonstrates clinically relevant abnormalities that may affect participant safety or interpretation of study results (eg, baseline QTcF interval  $>450$  msec, complete LBBB, signs of an acute or indeterminate-age myocardial infarction, ST-T interval changes suggestive of myocardial ischemia, second- or third-degree AV block, or serious bradyarrhythmias or tachyarrhythmias).

If QTcF exceeds 450 msec, or QRS exceeds 120 msec, the ECG should be repeated 2 more times and the average of the 3 QTcF or QRS values should be used to determine the participant's eligibility. Computer-interpreted ECGs should be overread by a physician experienced in reading ECGs before excluding participants.

18. Participants with **ANY** of the following abnormalities in clinical laboratory tests at screening, as assessed by the study-specific laboratory and confirmed by a single repeat test if deemed necessary:

- AST or ALT level  $\geq 1.5$  times ULN;

- Total bilirubin level  $\geq 1.5$  times the ULN; participants with a history of Gilbert's syndrome may have direct bilirubin measured and would be eligible for this study provided the direct bilirubin level is  $\leq$  ULN;
- TSH > ULN;
- Fasting C-peptide <0.8 ng/mL;
- Serum calcitonin > ULN;
- Amylase > ULN;
- Lipase > ULN;
- eGFR <60 mL/min/1.73m^2 as calculated by MDRD equation;
- FPG >270 mg/dL at **screening or admission**.

**Other Exclusions:**

19. History of alcohol abuse or binge drinking and/or any illicit drug use or dependence within 6 months of Screening.

**Note:** Binge drinking is defined as a pattern of 5 (male) and 4 (female) or more alcoholic drinks in about 2 hours. As a general rule, alcohol intake should not exceed 14 units per week (1 unit = 8 ounces ([240 mL] beer, 1 ounce [30 mL] of 40% spirit or 3 ounces [90 mL] of wine).

20. Blood donation (excluding plasma donations) of approximately 1 pint (500 mL) or more within 60 days prior to dosing.

21. History of sensitivity to heparin or heparin induced thrombocytopenia, if heparin is used to flush IV catheters.

22. Known intolerance to any GLP-1R agonist.

23. Unwilling or unable to comply with the criteria in the [Lifestyle Considerations](#) section of this protocol, including restrictions on caffeine, alcohol and tobacco use.

24. Investigator site staff members directly involved in the conduct of the study and their family members, site staff members otherwise supervised by the investigator, or Pfizer employees, including their family members, directly involved in the conduct of the study.

**5.3. Lifestyle Considerations**

The following guidelines are provided:

### 5.3.1. Meals and Dietary Restrictions

- Participants must abstain from all food and drink (except water) at least 8 hours prior to the blood sample collection at the outpatient **Screening** and on-site **follow-up** visits.
- Participants are required to fast for 4 hours (except water) prior to **admission** to CRU.
- Participants must abstain from all food and drink (except water) at least 8 hours prior to the first blood sample on inpatient study days [eg, for FSBG, safety laboratory, PK, or PD assessment].
- Noncaffeinated drinks (except as indicated below) may be consumed with meals and the evening snack.
  - Participants will refrain from consuming red wine, grapefruit, or grapefruit-related citrus fruits (eg, Seville oranges, pomelos, grapefruit juices) from 7 days prior to the first dose of investigational product until collection of the final PK blood sample.
- The initial caloric intake/menu assigned to each participant will be based on the Harris Benedict formula (sedentary lifestyle; to be provided to the site prior to study start) using the participant's body weight measured at screening.
- **Breakfast** will be provided at approximately 0800 hours on each inpatient day:
  - A standard breakfast will be provided for consumption after dosing on all days except those when liquid meal (for MMTT) is administered;
  - On days where liquid meal is administered, in lieu of breakfast, the meal will be provided as 16 ounces of Ensure Plus® and will be administered as listed in the [SoA](#). The entire Ensure Plus® meal is to be consumed within 10 minutes (See [Section 8.9.1](#)).
- **Lunch** will be provided approximately 4 hours after dosing (approximately 1200 hours) and at approximately the same time on each inpatient day. On days with liquid meal for breakfast, lunch will be provided after the 4-hour post-dose blood collection samples for the MMTT have been completed.
- **Dinner** will be provided approximately 10 hours after dosing (approximately 1800 hours) and at approximately the same time on each inpatient day.
- An **evening snack** may be permitted at approximately 2200 hours on non-MMTT days. On days when the MMTT is performed, an evening snack will be provided.
  - On days with MMTT as listed in the [SoA](#) (including the evening prior to MMTT) participants will be encouraged to consume all provided food, including the liquid

meal and all standard meals and snacks provided on these days. Meals on these days will be standardized such that participants receive the same menus for all meals on these days (including the evening prior).

- If participants do not consume their entire meal on Day -1, they will be instructed to consume the same amount of food ( $\pm 10\%$ ) on the other days with MMTT that they ate on Day -1.
- The start time of all meals (including liquid Ensure Plus™ meal) on these days will be noted in the CRU source documents and should be available to the sponsor on request. Participants will be encouraged to eat all standard meals within 30 minutes on days with liquid meal administration.
- Participants will receive the same snack each evening prior to the MMTT the following day. On these days, participants will be encouraged to consume the entire evening snack.
- Participants will not be required to consume all provided food during standard meals on other study days.
- When a meal or snack is scheduled at the same time as an ECG, the meal will be provided after the ECGs are completed.
- Details on the meals provided to participants including the menu items, portion sizes, and approximate calories with nutritional macronutrient (% carbohydrate, fat and protein) breakdown of the meal will be maintained in source documentation at the CRUs. This information will not be collected in the case report form; however, it may be submitted to the sponsor on request. The approximate percentage of food consumed (based on visual inspection by the site staff) should likewise be recorded in CRU source documents.

### 5.3.2. Caffeine, Alcohol, and Tobacco

- Participants will abstain from alcohol for 24 hours (or as specified above for red wine) prior to **admission** to the CRU and continue abstaining from alcohol until collection of the final blood sample at the **follow-up** visit. Participants may undergo an alcohol breath test or blood alcohol test at the discretion of the investigator.
- Caffeine-containing products, up to the equivalent of two 8-ounce cups of coffee per day, will be permitted.
  - **However**, participants must abstain from caffeine-containing products for a minimum of 2 hours prior to all vital signs and ECG measurements conducted throughout study participation (from screening to the final follow-up visit).
  - On days when MMTT is conducted, participants may ingest caffeine-containing products (up to the equivalent of two 8-ounce cups of unsweetened black coffee

per day). This may be permitted provided that there are no additional calories consumed and there is no anticipated impact to the MMTT data, that is no sugar, sweetener, flavorings, milk, cream etc.

- Participants may use tobacco- or nicotine-containing products as permitted by the CRU (eg, during smoking breaks, or in specified locations).

**However**, smoking may not be permitted when it would interfere with the timing of scheduled study procedures or during frequent sampling procedures (eg, MMTT). In addition, participants must abstain from use of tobacco- or nicotine-containing products:

- For a minimum of 2 hours prior to all vital sign and ECG measurements;
- For a minimum of 2 hours prior to and following administration of investigational product.

### 5.3.3. Activity

- Participants will abstain from strenuous exercise (eg, heavy lifting, weight training, calisthenics, aerobics) for at least 48 hours prior to each blood collection for clinical laboratory tests. Walking at a normal pace will be permitted.
- In order to standardize the conditions on PK sampling days, participants will be required to refrain from lying down (except when required for BP, pulse rate, and ECG measurements), eating, and drinking beverages other than water during the first 4 hours after dosing.

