Urine Sampling for:																										
- Urine drug test	x	x																								
- Urinalysis (and microscopy, as appropriate)	x						x		x							x						x	x		x	

- a. This follow-up contact may be conducted as a phone call.
- b. Full physical exam at times indicated; limited exam for previous findings, new/open AEs, or investigator discretion.
- c. Enquire about exposure to positive participant, residence or travel in area of high incidence and check for COVID-19 related signs and symptoms.
- d. The testing for COVID-19 pathogen by PCR will be performed at Screening and Admission. At Admission, testing will be done prior to confinement. Additional testing may be conducted at the discretion of the investigator.
- e. To be done at least daily during residence.
- f. Single 12-lead ECG at Screening, follow-up and Early Termination (if applicable). Measure in triplicate at all other times indicated.
- g. Measurement/sample at 0H corresponds to the 24H timepoint as detailed in [Table 2](#) (ie, listed in both tables, but only one sample/measurement should be collected).
- h. Single vital signs at Screening, follow-up and Early Termination (if applicable). Measure in triplicate at all other times indicated.
- i. Fingertick glucose via glucometer on admission to CRU and prior to breakfast on all inpatient days; may be more frequent at the discretion of the investigator.
- j. Meals to be provided on all days while inpatient at approximately 0H, 4H, and 10H relative to dosing; snacks may be provided. Refer to [Section 5.3](#).
- k. This procedure is to be conducted in participants enrolling with T2DM only.
- l. Dose administration to occur with breakfast or liquid meal daily on Days 1 to 42, inclusive, see [Section 5.3](#) and [Section 6](#).
- m. See [Appendix 2](#) for safety lab tests to be collected at each timepoint, see [Section 5.3](#) for fasting requirements. Note: C-peptide is collected as part of safety labs at Screening.
- n. FSH in females to confirm postmenopausal status only.
- o. PK samples on Day 43, 44, and 45 are to be collected 24H, 36H, 48H, and 72H after the final PF-07081532 dose on Day 42.

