**Table 2. Detailed Schedule (selected study days)**

	Study Day	Hours Relative to Dosing at 0H a													
		0	0.25	0.5	1	1.5	2	3	4	6	8	10	12	16	24 b
Triplicate, supine 12-lead ECG	Days -1, 1, and 42	x			x		x		x		x		x		x
Triplicate, supine vital sign (blood pressure and pulse)	Days -1, 1, and 42	x			x		x		x		x		x		x
Fasting fingerstick blood glucose measurement b,c	All inpatient days	x													
Liquid meal (for MMTT) d	Days -1, 28 e and 42	x													
Standardized meal/snack f	all inpatient days	x g							x			x		x	
Blinded investigational product administration	Daily: Day 1 to Day 42	x h													
Blood sampling for:															
- Safety laboratory tests i	Days -1, 28, and 42	x j													
- HbA1c k , TSH	Days -1, 28, and 42	x j													
- Plasma glucose l	Days -1, 28 e and 42	x j	x	x	x	x	x	x	x	x	x	x	x	x	x
- Plasma insulin l	Days -1 and 42	x j, m	x	x	x	x	x	x	x						
- Plasma C-peptide k , glucagon k )	Days -1 and 42	x j	x	x	x	x	x	x	x						
- Free T4, calcitonin, amylase, lipase, lipids	Days -1, 28, and 42	x j													
- PF-07081532 PK	Days 1 and 42	x		x	x		x		x	x	x	x	x	x	x
- 4-β-hydroxycholesterol/cholesterol	Days 1 and 42	x													
- Retained research samples for Prep D1.5	Day -1 only n	x													
- Retained research samples for Prep B1.5 and Prep B2.5	Day -1 and Day 42	x													
Urine sampling for:															
- Urinalysis and microscopy, as appropriate	Days -1, 28, and 42	x													

- On Day -1, time of 0H procedures to match approximate planned clock time of collection on Day 1. All other days, 0H procedures to be completed pre-dose.
- The 24H sample is to be collected prior to dosing on the following morning, as indicated in [Table 1](#).
- Fingerstick glucose via glucometer on admission to CRU and prior to breakfast on all inpatient days; may be more frequent at the discretion of the investigator.
- Liquid meal given at 0H (or on Day -1 at the anticipated clock time of Day 1 dose) to be consumed over 10 mins. The 0.25 H sample is 5 minutes after completion of the liquid meal. This procedure is to be conducted in participants enrolling with T2DM only.

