- Indicated procedures will be conducted on Days -1, 28, and 42 for Cohort 1; decision for Day 28 procedures in subsequent cohorts will be provided in writing prior to initiation of dosing for each cohort.
- Standardized meals/snacks to be provided on all days while inpatient; identical meals/snacks on days when MMTT is being conducted. Refer to [Section 5.3](#).
- Standard breakfast NOT provided on days when MMTT is being conducted; refer to [Section 5.3](#).
- Dosing to occur with breakfast or liquid meal daily from Day 1 to day 42, inclusive.
- See [Appendix 2: Clinical Laboratory Tests](#) for safety lab tests to be collected at each timepoint.
- See [Section 5.3](#) for fasting requirements.
- Participants enrolling with T2DM only.
- Fasting (0H) sample is to be collected in all participants. Post-dose timepoints in participants enrolling with T2DM only.
- Fasting (time 0H only) insulin to be measured in triplicate on Day -1 and Day 42, all other measurements single, see [Section 8.9.2](#).
- If not collected on the designated collection day, collect at the next available time point when biospecimens are being collected in conjunction with a participant visit.

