#### 6.1.1. Administration

On Day 1, participants will receive IP at approximately 0800 hours (plus or minus 2 hours). Dosing of IP is planned to occur in the fed state, ie, with breakfast. Details on meals and dietary requirements and activity restrictions are given in [Lifestyle Considerations](#) section of the protocol. Investigator site personnel will administer investigational product with approximately 240 mL ambient temperature water. Participants will swallow the investigational product whole, and will not manipulate or chew the investigational product prior to swallowing.

- Blinding will be maintained by keeping the number of tablets the same for PF-07081532 and placebo within a given cohort.

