- Breakfast: provided for consumption following dosing, where applicable (see [Section 5.3.1](#)).

Safety/laboratory/analyte results obtained following 1st dose of the study intervention (Day 1) that could unblind the study (ie, glucose, insulin, glucagon, C-peptide, HbA1c, and PK), will not be reported to investigative sites or other blinded personnel until the study has been unblinded.

If an IV catheter is utilized for blood sample collections, ECGs and vital sign assessments (pulse rate and BP) should be collected prior to the insertion of the catheter.

For samples being collected and shipped, detailed collection, processing, storage, and shipment instructions and contact information will be provided to the investigator site prior to initiation of the study.

The total blood sampling volume for individual participants is approximately, *up to* 425 mL. If participants with obesity are enrolled, approximately, *up to* 245 mL blood will be collected. The actual collection times of blood sampling may change. Additional blood samples may be taken for safety assessments at times specified by Pfizer, provided the total volume taken during the study does not exceed 550 mL during any period of 56 consecutive days.

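### Protocol 5.3.3 bars food for 4 hours after dosing on PK sampling days without mentioning the dosing meal, and Cohort 1's exploratory accumulation ratio compares different doses and meals

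*Protocol*

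**What the plan says.** **Food around dosing.** Protocol 5.3.3 sets conditions for PK sampling days. Participants must not lie down, except for blood pressure, pulse and ECG measurements, and must refrain from "eating, and drinking beverages other than water during the first 4 hours after dosing". No exception is given for the meal taken with the dose. Elsewhere the Protocol says:

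- Table 1, footnote l: "Dose administration to occur with breakfast or liquid meal daily on Days 1 to 42, inclusive". A footnote to Table 2 repeats this.
- Section 6.1.1: "Dosing of IP is planned to occur in the fed state, ie, with breakfast".
- Section 5.3.1: "A standard breakfast will be provided for consumption after dosing on all days except those when liquid meal (for MMTT) is administered".
- Section 8, order of procedures: breakfast is "provided for consumption following dosing, where applicable".
- Table 2, liquid-meal footnote (T2DM participants only): "Liquid meal given at 0H (or on Day -1 at the anticipated clock time of Day 1 dose) to be consumed over 10 mins". Day 42 is one of these days.

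**Accumulation ratio.** Protocol 4.3 fixes Cohort 1 at 20 mg daily for 28 days and then 60 mg daily for 14 days. Protocol Table 5 defines Rac as steady-state dose-normalised AUC24 over Day 1 dose-normalised AUC24, assigns it to Day 42, builds Rac,Cmax in the same way, and classes both as exploratory. SAP 6.3.1 fits a one-way ANOVA to the log ratios with dose as the only term, and reports the back-transformed means and 90% CIs as accumulation by dose. Protocol 9.3.3 treats each cohort as its own treatment.

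**The concern.** There are two separate issues.

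First, 5.3.3 exists to standardise conditions on PK days, yet it cannot be followed together with the meal instructions. Serving the meal breaches 5.3.3. Withholding it breaches the other sections. Days 1 and 42 supply the secondary PK endpoints, so the written conditions for those days should agree.

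Second, an accumulation ratio is normally read as the effect of repeated dosing at a fixed dose under like conditions. In Cohort 1 the numerator and denominator differ threefold in dose and, for T2DM participants, in the meal. Dose normalisation removes the dose difference only if exposure is proportional to dose, and nothing in the analysis removes a meal difference. Any non-proportionality or meal effect would be reported as accumulation.

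**Working it through.** **Meal passages side by side.** The 5.3.3 rule covers PK sampling days in general. Table 2 places full PK profiles on Days 1 and 42. Counting the PK row of Table 1 against its day header gives further samples on Days 2, 8, 14, 22, 29 and 36, taken at 0H by default. The ECG, vital-sign and weight rows show the same pattern at Days 8, 14, 22 and 29. All of these are dosing days with breakfast or a liquid meal, so the literal conflict reaches all of them.

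**What Cohort 1 Rac contains.** The scheme covers 28 + 14 = 42 days, so Day 1 is 20 mg and Day 42 is 60 mg, a ratio of 60/20 = 3. Table 2 sets the mixed-meal test in Cohort 1 on Days -1, 28 and 42. Day 1 is therefore a standard-breakfast day and Day 42 a liquid-meal day in T2DM participants. If exposure scales as dose^b and the meal change multiplies exposure by m:

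observed Rac = true accumulation × 3^(b−1) × m

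The documents give neither b nor m. With m left at 1 and b assumed:

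| b | 3^(b−1) |
|---|---|
| 0.8 | 0.80 |
| 0.9 | 0.90 |
| 1.0 | 1.00 |
| 1.1 | 1.12 |
| 1.2 | 1.25 |

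**Is a constant-dose check available from scheduled samples?** In Cohort 1 every dose on Days 1 to 21 is scheduled at 20 mg on a standard-breakfast day. The Day 2 0H sample follows one dose, and the Day 22 0H sample follows 21 doses (21 × 24 = 504 h). The fraction of steady state reached is 1 − 2^(−504/t½). This is above 99.9% for a half-life of 48 h or less, 99.2% at 72 h and 97.0% at 100 h (half-lives assumed).

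**Precision of that trough ratio.** For one cohort of 9 on active treatment (8 df), the 90% CI multiplier is exp(± t(0.95, 8) × √ln(1+CV²) / √9), with t = 1.860 and CV that of the ratio. At CV 50%, √ln(1.25) = 0.472 and 1.860 × 0.472 / 3 = 0.293, which gives ×0.75 to ×1.34. At 30% it is ×0.83 to ×1.20, and at 70% ×0.68 to ×1.48. The CVs are assumptions.

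**Agreement with an AUC ratio.** The check uses a linear one-compartment model with first-order absorption and constant dosing every 24 h. Each cell gives AUC24 Day 42/Day 1, then trough Day 22/Day 2:

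| t½ | ka 0.2/h | ka 0.5/h | ka 1.0/h |
|---|---|---|---|
| 12 h | 1.53, 1.34 | 1.39, 1.33 | 1.36, 1.33 |
| 24 h | 2.40, 2.02 | 2.13, 2.00 | 2.06, 2.00 |
| 48 h | 4.19, 3.44 | 3.68, 3.41 | 3.54, 3.41 |

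The trough ratio is 2–7% below the AUC ratio at ka 0.5–1.0/h, and 12–18% below it at ka 0.2/h.

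**The case against.** **On the meal rule.** Section 5.3.3 is headed Activity. Meals belong to 5.3.1, to which Section 8 refers for breakfast, and several consistent passages point to fed dosing. With lunch at about 4 hours after the dose, a natural reading is that no further food is taken until lunch. This stands as to evident intent, but 5.3.3 does not say it. A reader might go further and infer that participants could be dosed fasted, or that AUC24, Cmax or Tmax is compromised. The documents do not support that: five other places call for a meal at dosing, and no effect on these endpoints can be shown from the text.

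**On Rac.** Dose normalisation is the prespecified handling for a titration design. The proportionality assumption is visible in the definition, and the planned dose-normalised plots let a reader look at it. Redacted text or the earlier studies may settle proportionality. All of this stands, and it is why no bias is claimed. It does not address the meal difference, and the results are still to be reported simply as accumulation.

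**On the ANOVA term.** A reader might infer that cohorts sharing a Day 42 dose but starting at different doses will be pooled. Protocol 4.3 allows later cohorts different starting doses, but their schemes are not shown. SAP 6.3.1 also appears to use dose and treatment interchangeably, and Protocol 9.3.3 makes the cohort the unit. Pooling is only a possibility, and the wording is loose.

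**On the trough ratio.** It rests on two single samples. Its departure from an AUC ratio (2–18% in the illustration) is of a similar order to the distortion it is meant to check. SAP 5.3.1 sets BLQ values to zero, so a BLQ Day 2 trough would make it undefined. SAP 5.3.3 excludes data only from the day of an off-scheme dose, which does not secure constant dosing before a trough. These objections stand. They limit the ratio to a supplement and require the two rules given in the fix.

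**Conclusion.** Both parts hold, and both are minor.

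1. The instructions on food around dosing contradict one another as written on Days 1 and 42 and on the trough days in Table 1. This is a wording conflict with no demonstrated effect on any endpoint.
2. In Cohort 1, Rac and Rac,Cmax measure accumulation only under dose proportionality between 20 and 60 mg and equivalence of the two meals. The visible text establishes neither. The factor of 0.80 to 1.25 rests on assumed exponents of 0.8 to 1.2 and is an illustration. It would be wrong to read it as a known bias in either direction, and no meal effect is quantified.

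The threefold step is fixed for Cohort 1 only, and the meal difference applies to T2DM participants only. Rac is exploratory, no hypothesis is tested, and no primary endpoint or sample-size figure is touched.

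**What to change.** **Protocol.** Reconcile 5.3.3 with 5.3.1, 6.1.1, Section 8 and the footnotes to Tables 1 and 2 on food around dosing on PK sampling days. Which rule applies is for the sponsor to settle.

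**SAP 6.3.1.**

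- Where the scheduled dose differs between Day 1 and Day 42, add a supplementary constant-dose trough accumulation ratio. For Cohort 1 this is Day 22 0H over Day 2 0H.
- Limit it to participants who received the assigned dose on all preceding days used (Days 1 to 21 in Cohort 1).
- Treat the ratio as not calculated when the Day 2 trough is BLQ, and report how many are lost this way.
- Footnote Rac and Rac,Cmax with the proportionality and meal assumptions.
- Label the ANOVA term as cohort/treatment, in line with Protocol 9.3.3.

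**Cost.** A protocol clarification, some SAP wording and one derived ratio. No new samples are needed, and SAP 6.3.1 already plots median troughs over the whole study. The ratio is imprecise and is not identical to an AUC ratio, so it supplements Rac and Rac,Cmax and does not replace them. Dropping BLQ denominators removes participants with the lowest Day 2 troughs. In later cohorts the usable days depend on the dosing scheme.
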